If DLTs are observed in the first two consecutive patients of a previously untested dose level, subsequent enrolment to that cohort will be stopped. The BLRM will be re-run to confirm that the dose level still fulfils the EWOC principle. Based on this information, the SRC will evaluate whether the next patients will be enrolled at the same dose level, or if they will be enrolled at a lower dose level.

The SRC may recommend stopping the dose-finding phase after the criterion for MTD (Section 7.1) is fulfilled. Further patients may be included to confirm this MTD estimate, i.e., to confirm that the EWOC criterion is still fulfilled. If no DLT is observed at a dose at which the efficacy is considered sufficient, the SRC may decide to include an additional number of patients at the same dose level and to declare this dose as the recommended dose for further development (RP2D). The SRC can declare any dose that fulfils the EWOC criterion as RP2D, independent of the MTD estimate.

Following determination of the MTD and/or RP2D from the Phase Ia portion, separate cohorts of approximately 30-40 patients each will be conducted in patients with select advanced solid malignancies including tumours with specific histology/tumour types and/or specific genetic profiles as specified in the following cohorts:

- Cohort 4: Solid tumours including NSCLC, bladder cancer, melanoma, gastric cancer, ovarian cancer, triple-negative breast cancer, and renal-cell cancer
- Cohort 5: Tumours with high TMB excluding those with high microsatellite instability (MSI-high)
- Cohort 6: Refractory squamous cell cervical, anal, and skin tumours
- Cohort 7: Recurrent human papillomavirus (HPV)-positive, or HPV-negative, vaginal or vulvar squamous cell carcinoma (VSCC)

The Phase Ib portion of the trial will further evaluate the safety, tolerability, efficacy, PK profile, and biomarkers of BI 754091.

The analysis of the squamous cell tumour cohort (Cohort 6) and the VSCC cohort (Cohort 7) will follow a two-stage approach.

The interim analysis for Cohort 6:

- Squamous cervical and/or anal cancer, Stage 1 will include 10 treated patients.
- Squamous skin tumours, Stage 1 will include 10 treated patients.

The interim analysis for Cohort 7:

- Vaginal or VSCC, Stage 1 will include 20 treated patients.

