 - Mean resting corrected QT interval (QTc) >470 msec
 - Any clinically important abnormalities (as assessed by the Investigator) in rhythm, conduction, or morphology of resting ECGs, e.g., complete left bundle branch block, third degree heart block
 - Any factors that increase the risk of QTc prolongation or risk of arrhythmic events such as heart failure, hypokalaemia, congenital long QT syndrome, family history of long QT syndrome or unexplained sudden death under 40 years-of-age, or any concomitant medication known to prolong the QT interval
 - Ejection fraction (EF) <55% or the lower limit of normal of the institutional standard will be excluded. Only in cases where the Investigator (or the treating physician or both) suspects cardiac disease with negative effect on the EF will the EF be measured during screening using an appropriate method according to local standards to confirm eligibility (e.g., echocardiogram [ECHO], multi-gated acquisition scan [MUGA]). A historic measurement of EF no older than 6 months prior to first administration of study drug can be accepted provided that there is clinical evidence that the EF value has not worsened since this measurement in the opinion of the Investigator or of the treating physician or both.
9. History of pneumonitis within the last 5 years
10. History of severe hypersensitivity reactions to other mAbs
11. Immunosuppressive corticosteroid doses (>10 mg prednisone daily or equivalent) within 4 weeks prior to the first dose of BI 754091
12. Active autoimmune disease or a documented history of autoimmune disease, except vitiligo or resolved childhood asthma/atopy
13. Known history of human immunodeficiency virus infection or an active hepatitis B or C virus infection. HIV infection is allowed for patients in cohort 6 (cervical/anal squamous) and cohort 7 (vulvar).
14. Interstitial lung disease
15. Chronic alcohol or drug abuse or any condition that, in the Investigator's opinion, makes him/her an unreliable trial subject, unlikely to complete the trial, or unable to comply with the protocol procedures.

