6.2.1.3 Medical history

History of the patient's cancer will be obtained. The type of cancer, the date of the first histological diagnosis (month and year may be sufficient), and the primary tumour site will be reported on the eCRF. The differentiation grade (not specified, undifferentiated, poorly differentiated, moderately differentiated, well differentiated) obtained at the time of diagnosis and the location of metastatic sites as well as the stage according to the tumour, (lymph) node, metastasis (TNM) classification will be provided as obtained at diagnosis and at trial screening. Previous surgeries will be reported.

Previously administered chemotherapy, tyrosine kinase inhibitor treatment, vaccine therapy, antibodies therapy, immune therapy, and hormone therapy will be reported, including start and end dates (month and year may be sufficient), as well as whether therapy was given as

neoadjuvant, adjuvant, or palliative therapy. The date of tumour progression after previous line of treatment will be recorded, if known.

Baseline information relevant to the disease history such as PD-L1 expression level, microsatellite instability (MSI), and tumour mutation burden (TMB) information will be collected in eCRF where available.

Exclusion Criterion #13 (see Section 3.3.3) does not apply to the patients with cervical/anal and vulvovaginal cancer enrolling into Cohorts 6 and 7. However, virology testing should still be done and the status of HIV and hepatitis B or C virus should be collected on the eCRF.

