Rationale for change	To clarify exclusion of other active cancers and to align language across current studies with BI 754091

Section to be changed	Section 3.3.3 Exclusion Criteria
Description of change	
9. Any of the following cardiac criteria:
 
 - Mean resting corrected QT interval (QTc) >470 msec - Any clinically important abnormalities (as assessed by the Investigator) in rhythm, conduction, or morphology of resting ECGs, e.g., complete left bundle branch block, third degree heart block - Any factors that increase the risk of QTc prolongation or risk of arrhythmic events such as heart failure, hypokalaemia, congenital long QT syndrome, family history of long QT syndrome or unexplained sudden death under 40 years-of-age, or any concomitant medication known to prolong the QT interval - Ejection fraction (EF) <55% or the lower limit of normal of the institutional standard will be excluded. Only in cases where the Investigator (or the treating physician or both) suspects cardiac disease with negative effect on the EF will the EF be measured during screening using an appropriate method according to local standards to confirm eligibility (e.g., echocardiogram [ECHO], multi-gated acquisition scan [MUGA]). A historic measurement of EF no older than 6 months prior to first administration of study drug can be accepted provided that there is clinical evidence that the EF value has not worsened since this measurement in the opinion of the Investigator or of the treating physician or both. Ejection fraction <55% or the lower limit of normal of the institutional standard.
Rationale for change	To clarify exclusion of other active cancers and to align language across current studies with BI 754091
Section to be changed	Section 3.3.3 Exclusion Criteria
Description of change	
13 Known history of human immunodeficiency virus infection or an active hepatitis B or C virus infection (exception: this criteria does not apply to patients with cervical/anal tumours enrolling in Cohort 6)

Rationale for change	Due to the high incidence of HIV in patients with cervical and anal cancers, and no anticipated safety concerns exist for including such patients in the trial, Exclusion Criterion #13 (see Section 3.3.3) does not apply to the patients with cervical/anal cancer enrolling into Cohort 6.
Section to be changed	Section 3.3.4.2 Discontinuation of the trial by the sponsor

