Description of change	Pre- and on-treatment tumour biopsy collections for biomarker and PD _c analyses will be mandatory from all patients in the Phase Ib dose-expansion portion of the trial. In addition, an optional biopsy biopsies should be taken according to the flowchart and Section 5.5.2.3 after treatment discontinuation, if possible.
Rationale for change	To clarify the expectations regarding biopsy collection.
Section to be changed	
Description of change	

Rationale for change		
Section to be changed	Section 6.2.1.1 Screening for tumour mutational burden (TMB) and MSI-high cohort	
Description of change	
For Cohort 5, the TMB, as well as the microsatellite stability (MS) status have to be assessed. Patients that have high TMB (defined as ≥ 20 mutations/Mb) and are MS stable (MSS) will be included. Whereas for MS status determination any validated assay may be used, the TMB has to be measured by [REDACTED] (FM). Patients may be included that fulfil the criteria (1) having undergone testing by FM previously; (2) if evidence is available that the criteria may be fulfilled (or with sponsor approval) after providing archival tumour material (as specified in the lab manual) and testing by FM; or (3) if evidence is available that the criteria may be fulfilled, after providing an additional fresh tumour biopsy and testing by FM. Options 2 and/or 3 may be discontinued at the sponsor's discretion.
 
If polymerase epsilon (ϵ) catalytic subunit (POLE) mutation status is known for any patient in the TMB-high cohort, this information should be collected.
	
Rationale for change	Details for determining TMB are added and information about collecting available POLE information is added in this new section of the protocol Subsequent sections are renumbered accordingly.	
Section to be changed	Section 6.2.1.3 Medical history	
Description of change	[...] Exclusion Criterion #13 (see Section 3.3.3) does not apply to the patients with cervical/anal cancer enrolling into Cohort 6. However, virology testing should still be done and the status of HIV and hepatitis B or C virus should be collected on the eCRF.	
Rationale for change	To clarify that although patients with HIV may be enrolled into Cohort 6, virology testing should still be performed with results recorded in the eCRF.	
Section to be changed	Section 6.2.3.4 Overall survival visits (new section added)	

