Description of change	
7. Females of childbearing potential willing to use adequate contraceptive measures from the time of screening until 6 months after trial discontinuation, who are not or will not be breast feeding, and agree to have pregnancy tests prior to the start of dosing and at regular visits during the trial. Females not of childbearing potential must have evidence of such by fulfilling one of the following criteria at screening:
 
 For women of childbearing potential using a contraceptive pill, an additional barrier method is necessary. A list of adequate contraception methods is provided in the patient information. Acceptable highly effective methods of contraception include total sexual abstinence when this is in line with the preferred and usual lifestyle of the study participant (periodic abstinence such as calendar, ovulation, symptothermal, post-ovulation methods and withdrawal are not acceptable methods of contraception), an intrauterine device or intrauterine hormone-releasing system, bilateral tubal ligation, and vasectomised partner (with post-vasectomy proof of absence of sperm)
Rationale for change	Appropriate contraception methods are defined.
Section to be changed	Section 3.3.3 Exclusion criteria

Proprietary confidential information © 2023 Boehringer Ingelheim International GmbH or one or more of its affiliated companies

Description of change	13. Known history of human immunodeficiency virus infection or an active hepatitis B or C virus infection. HIV infection is allowed for patients in cohort 6 (cervical/anal squamous) and cohort 7 (vulvar). (exception: this criteria does not apply to patients with cervical/anal tumours enrolling in Cohort 6)
Rationale for change	To clarify that patients with HIV may enroll on Cohort 6 and Cohort 7.
Section to be changed	Section 4.1.9 Administration of doses for each patient
Description of change	Sites will provide normal saline (sodium chloride 0.9%) for the dilution of study drug. For sites in the UK, the saline must be an EU licensed product.
Rationale for change	To provide further details about drug dilution
Section to be changed	Section 4.2.3.2 Restrictions regarding women of childbearing potential

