	A2.2	Intake of restricted medications or any drug considered likely to interfere with the safe conduct of the trial	Exclusion criteria 2 met	None Automatic
	A2.3	Previous enrolment in this trial	Exclusion criteria 3 met	None Automatic
	A2.4	Use of investigational or antitumour treatment within 30 days prior to the initial administration of BI 754091	Exclusion criteria 4 met	None Automatic
	A2.5	History within the last 5 years of an invasive malignancy other than the one treated in this trial. Refer to protocol for the exception.	Exclusion criteria 5 met	None Automatic
	A2.6	Untreated brain metastasis(es) that may be considered active.	Exclusion criteria 6 met	None Automatic
	A2.7	Inadequate organ function or bone marrow reserve as demonstrated by the laboratory values in CTP Section 3.3.3	Exclusion criteria 7 met	None Automatic
	A2.8	Improper cardiac criteria according to CTP Section 3.3.3	Exclusion criteria 8 met	None Automatic
	A2.9	History of pneumonitis within the last 5 years	Exclusion criteria 9 met	None Automatic
	A2.10	History of severe hypersensitivity reactions to other mAbs	Exclusion criteria 10 met	None Automatic
	A2.11	Immunosuppressive corticosteroid doses (>10 mg prednisone daily or equivalent) within 4 weeks prior to the first dose of BI 754091	Exclusion criteria 11 met	None Automatic
	A2.12	Active autoimmune disease or a documented history of autoimmune disease, except vitiligo or resolved childhood asthma/atopy	Exclusion criteria 12 met	None Automatic

Table 6.2: 1 Important protocol deviations (cont.)

Category / Code	Description	Comment / Example	Excluded from	Automatic/ Manual	
A					
	A2.13	Known history of human immunodeficiency virus infection or an active hepatitis B or C virus infection	Exclusion criteria 13 met	None	Automatic
	A2.14	Interstitial lung disease	Exclusion criteria 14 met	None	Automatic
B		Informed consent			
	B1	Informed consent not available/not done	Inclusion criteria 1 not met	None	Automatic
	B2	Informed consent too late	Inclusion criteria 1 not met- Informed consent obtained later than the initiation of treatment	None	Automatic
C		Trial medication			
	C1.1	Non-compliance with BI 754091 per protocol	Incorrect trial medication dose taken or wrong dose schedule, i.e. wrong infusion time; this will be the decision at MQRM	None	Automatic and manual

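### Protocol Section 6.2.1.3 lifts all of Exclusion 13 for Cohort 6 cervical/anal and Cohort 7 patients, but Section 3.3.3 lifts only HIV, so active hepatitis B or C is both barred and admitted

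*Protocol*

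**What the plan says.** **Protocol Section 3.3.3, Exclusion 13.** The criterion has two limbs: a known history of HIV, and active hepatitis B or C. The exception attached to it covers the first limb only: "HIV infection is allowed for patients in cohort 6 (cervical/anal squamous) and cohort 7 (vulvar". Nothing there relaxes the hepatitis limb for any cohort.

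**Protocol Section 6.2.1.3, Medical history.** This section points back to Section 3.3.3 and says that Exclusion 13 "does not apply to the patients with cervical/anal and vulvovaginal cancer enrolling into Cohorts 6 and 7". The sentence is not limited to HIV. The next sentence still asks for virology testing and for HIV and hepatitis B/C status on the eCRF, but gives no instruction to exclude on the result.

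**SAP Section 6.2, Table 6.2: 1, code A2.13.** The deviation is described as "Known history of human immunodeficiency virus infection or an active hepatitis B or C virus infection", with no cohort exception. Its trigger is "Exclusion criteria 13 met". It is marked as an automatic check and removes nobody from any analysis set.

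**The concern.** Both protocol sentences are current text, so this is a conflict between two live instructions and not between the body and the amendment log. In the visible text, Section 6.2.1.3 is the only place that asks for virology testing. A site with a positive hepatitis result is therefore likely to read the sentence that sets the criterion aside.

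A site following it would enrol a patient whom Section 3.3.3 bars for safety, in a trial of a drug with expected immune-related liver toxicity. Viral hepatitis also complicates the reading of liver events. DLTs are a Phase Ib primary endpoint, Grade 4 AST or ALT counts as a DLT without a viral exemption (Section 4.1.5), and a Hy's Law case requires that hepatitis B or C does not explain it (Section 5.3.6.5.4).

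**Working it through.** The plan gives no figure to reproduce. The check is to apply each section to each type of patient and then bound the number who could be affected.

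**1. The two sections side by side**

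| Patient | Section 3.3.3 | Section 6.2.1.3 |
|---|---|---|
| Cohort 6 cervical/anal, HIV | eligible | eligible |
| Cohort 6 cervical/anal, active hepatitis B or C | **ineligible** | **eligible** |
| Cohort 7 vulvar, HIV | eligible | eligible |
| Cohort 7 vaginal, HIV | ineligible if read literally (only vulvar is named) | eligible |
| Cohort 7 vaginal or vulvar, active hepatitis B or C | **ineligible** | **eligible** |

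The hepatitis rows are the main conflict. The vaginal HIV row is a smaller mismatch: Cohort 7 takes vaginal and vulvar disease (Section 3.3.2), but Exclusion 13 names only vulvar.

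**2. Intent** (amendment log, Protocol Section 11, used only for intent and dating)

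- The amendment 3 rationale for the Section 6.2.1.3 sentence speaks of HIV: "although patients with HIV may be enrolled into Cohort 6, virology testing should still be performed".
- The amendment 5 rationale for the present exception in Exclusion 13 also speaks of HIV: "To clarify that patients with HIV may enroll on Cohort 6 and Cohort 7". It names Cohort 7 as a whole, which supports covering vaginal as well as vulvar disease.
- Neither rationale argues for admitting active hepatitis.

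**3. Which patients would be deviations**

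Before amendment 5, Section 3.3.3 itself carried a blanket exception: "this criteria does not apply to patients with cervical/anal tumours enrolling in Cohort 6". For Cohort 6 cervical/anal patients enrolled then, the two sections agreed, and active hepatitis was not a deviation. Amendment 5 narrowed Section 3.3.3 to HIV and left Section 6.2.1.3 unrestricted while extending it to Cohort 7, which that amendment also introduced. The patients at issue are therefore all of Cohort 7, and Cohort 6 cervical/anal patients enrolled under amendment 5 or later.

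**4. Size of the groups**

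- Stage 1 (Section 3.1): "Squamous cervical and/or anal cancer, Stage 1 will include 10 treated patients", and 20 for vaginal or vulvar disease. 10 + 20 = 30.
- Maximum (Table 7.4: 1): 30 cervical/anal and 40 vaginal or vulvar. 30 + 40 = 70.

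These are planned group sizes, not counts of cases. They are upper bounds for the two scenarios as planned, because they include Cohort 6 patients enrolled before amendment 5, whose number is not given. The Stage 1 total also assumes that recruitment stops at exactly those sizes, although Section 3.1 does not require a pause during the interim analysis.

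**5. Would the SAP check find a case?**

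The SAP does not say what A2.13 reads.

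- If it reads the site's entry for criterion 13, a site that followed Section 6.2.1.3 could have recorded the criterion as not met, and the check would stay silent.
- If it reads the virology fields, it would find hepatitis cases but could also flag HIV-positive patients who are permitted.

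Manual code E1 in the same table, and confirmation of the final deviation list at the last report planning meeting before database lock, could still catch a missed case.

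**The case against.** **Section 3.3.3 governs.** It is the eligibility section and forbids entry if any listed criterion is fulfilled. Section 8.3.1 requires source evidence, before allocation, that none is. Section 6.2.1.3 concerns data collection and refers the reader to 3.3.3. This favours the HIV-only reading and is part of why the intent is clear. It does not cancel a sentence telling sites that the criterion does not apply.

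**Hepatic interpretation is already protected.** A reader might infer that liver events will be reported without viral status beside them. The documents do not support that. SAP Section 7.1, where baseline characteristics would be expected, is blacked out apart from a fragment, so absence cannot be concluded. Hepatitis status must be on the eCRF. Section 5.3.6.5.4 has the investigator, Medical Monitor and sponsor review potential Hy's Law cases, with viral hepatitis named as an alternative explanation. Exclusion 7 limits baseline ALT, AST and bilirubin, DLTs are classified after investigator and sponsor review, and hepatitis or transaminase elevation of Grade 2 or higher is an AESI. This objection largely stands.

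**The deviation check may work.** A reader might infer that A2.13 will miss these patients. That is only a possibility, for the reasons in step 5 of the working.

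**The number is unknown.** One could assume a hepatitis prevalence and calculate the chance of at least one case. The documents give no rate, do not say how many sites would follow Section 6.2.1.3, and do not say how many Cohort 6 patients preceded amendment 5. Such a figure would reflect its assumptions only. This objection stands in full.

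**Conclusion.** The conflict is real and stands in current text. For Cohort 6 cervical/anal and Cohort 7 patients with active hepatitis B or C, Section 3.3.3 says exclude and Section 6.2.1.3 says the criterion does not apply. The less safe instruction is the one that departs from the evident intent.

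The effect is small. At most 70 planned patients are in the affected groups (30 at the Stage 1 sizes), and the number with active hepatitis cannot be estimated. A patient is wrongly enrolled only if the hepatitis is active and the site followed Section 6.2.1.3.

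A reader might also infer that response rates or safety denominators are affected. They are not: A2.13 removes nobody, and efficacy and safety are analysed in the Treated Set. No analysis set or error rate changes. What is affected is patient safety, eligibility and the completeness of deviation reporting.

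**What to change.** **Wording**

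- Replace the sentence in Section 6.2.1.3 with: *Only the HIV part of Exclusion Criterion 13 is waived for Cohort 6 cervical/anal and Cohort 7 patients; active hepatitis B or C still excludes.*
- In Exclusion 13, write *vaginal or vulvar* for Cohort 7.

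With treatment ending by 31 August 2023, these edits serve mainly consistency.

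**Retrospective check**

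- Use the eCRF virology status, not only the site's criterion 13 entry, to list Cohort 6 cervical/anal and Cohort 7 patients with hepatitis B or C. Review each for active infection, since a recorded status alone may not establish it.
- Report under A2.13 the active cases in Cohort 7, and those in Cohort 6 cervical/anal enrolled under amendment 5 or later.
- Take viral status into account for every listed patient, including earlier Cohort 6 patients, when interpreting hepatic DLT, AESI and Hy's Law cases.

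Noting the HIV exception in the A2.13 row is an optional clarification.

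**Cost.** One sentence, one phrase and one listing with a short clinical review, using data that Section 6.2.1.3 already requires. No new data collection and no change to any analysis set.
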